#### 1.0 Background

Congenital idiopathic clubfoot is defined as "a complex foot deformity that occurs in an otherwise normal child" (Morcuende, Dolan, Dietz, & Ponseti, 2004). Despite idiopathic clubfoot being due to unknown causes and occurring in approximately every 1 in 1000 live births, it is often easily treated (Ansar et.al, 2018). Ignacio V. Ponseti was the leading pioneer in researching and treating clubfeet in infants and his methods are widely used today. "The Ponseti method is a safe and effective treatment for congenital idiopathic clubfoot and radically decreases the need for extensive corrective surgery" (Morcuende, Dolan, Dietz, & Ponseti, 2004). "This method involves weekly stretching of the deformity followed by application of a long-leg cast. All components of the deformity usually correct within 4 to 5 weeks with the exception of the equinus. A simple percutaneous tendoachilles tenotomy often is necessary to correct completely the equinus" (Morcuende, Dolan, Dietz, & Ponseti, 2004). "After the tenotomy, a final cast is applied and left in place for 3 weeks to allow for healing to occur in the correct position. When the last cast is removed, the patient is treated with abduction splinting with straightlast shoes and a Denis Browne-style bar set at 45 degrees external rotation for the normal foot and 70 degrees for the clubfoot. In bilateral cases both feet are set at 70 degrees of external rotation. The protocol for this foot abduction orthosis is 23 hours per day for the first 3 months and then nighttime only for 2 to 4 years. This process is essential to avoid recurrence" (Herzenberg, Radler, & Bor, 2002) "The goal of treatment is to correct all components of the deformity so that the patient has a pain-free. plantigrade foot with good mobility, without calluses, and without the need to wear special or modified shoes in the future" (Morcuende, Dolan, Dietz, & Ponseti, 2004). Several studies have supported Ponseti's methods of casting and discovered positive results, primarily avoiding Posteromedial Release (PMR), an extensive open surgery (Herzenberg, Radler, Bor, 2002). This treatment also resulted in a decreased number of patients whose clubfoot relapsed following treatment by the Ponseti method (Morcuende, Dolan, Dietz, & Ponseti, 2004).

One defining characteristic to Ponseti's method is the addition of the percutaneous Achilles Tenotomy a small procedure which has been shown to avoid PMR in 95% of cases. Because PMR was found to lead to long term stiffness and weakness and involved greater surgical intervention, the percutaneous Achilles tenotomy was implemented (Herzenberg, Radler, Bor, 2002). The percutaneous Achilles Tenotomy entails releasing the tendon with a scalpel blade and dorsiflexing the foot in order to correct the equinus, followed by the application of a long leg cast (Lebel et. Al, 2012) (Morcuende, Dolan, Dietz, & Ponseti, 2004). Percutaneous Achilles Tenotomies have been successfully performed in the operating room under general anesthesia and in an outpatient clinic setting utilizing local or topical anesthesia. Ponseti and others have performed the procedure as an in-office procedure under sterile conditions, yielding a rate of successful "nonsurgical" correction of clubfoot approaching 90% of cases." Performing this procedure in office has proven to be safe, yielding a low number of post-operative emergency room visits due to complications or parental concerns (Lebel et. Al, 2012). While studies have shown that in office percutaneous achilles tenotomies are safe and efficient, little has been done to investigate the pain management strategies implemented for infants during this procedure. As healthcare professionals working with infants, "the prevention of pain in neonates should held as highly as the treatment being provided not only because it is ethical, but also because research has proven that repeated painful exposures during early stages of life have the potential for deleterious consequences" (American Academy of Pediatrics, 2016). Those consequences include, but aren't limited to, "alterations in hemodynamic stability, altered stress hormone expression, heightened peripheral sensitivity, altered pain reactivity that persists following the painful stimulus, and somatization" (Stevens et. Al, 2014) One study identified the infant's ability to become conditioned to painful stimuli, such as heel lances, at as early as 3 days old (Taddio, Shah, Gilbert-MacLeod, & Katz, 2002). With this information in mind, healthcare providers should be prepared to provide adequate pain management for infants during painful procedures by utilizing non-pharmaceutical techniques, pharmaceutical techniques, or a combination of both.

During in office percutaneous Achilles tenotomies, several studies mention the use of topical anesthesia, such as EMLA, a Lidocaine/Prilocaine cream. This cream is applied to the infant's skin surrounding the heel cord and requires 30 minutes to provide numbness reaching a depth of up to 5 mm at maximum effect (Fox, Tobin, & Aria, 2016). Pershad, Steinberg, & Waters, 2008, study reported that a 5-gram tube of ELMA cream cost the hospital \$7.69, regardless of volume used from the tube. Other institutions have reported 25 grams of EMLA cream reaching \$56.00. Due to clinical observation and medical advancements, there is room to believe that time efficient and cost-effective methods of providing greater pharmaceutical pain management to clubfoot infants during this procedure are available.

The J-tip is a needle-free jet injection system that uses compressed CO2 instead of a needle to push .25 ml of lidocaine into the skin, providing a local anesthetic at the site of administration in less than a minute" (Lunoe, et al., 2015). The J-tip provides numbness to the site of application at a depth of 5- 8 mm (Fox, Tobin, & Aria, 2016). Pershad, Steinberg, & Waters, 2008, reported, in the same study referencing EMLA cream prices, that the Needle-free jet injection device price per cartridge and .25 mL of buffered Lidocaine cost the hospital \$2.10. Through various studies, the J-Tip has been proven to provide greater pain management than other pharmaceutical options, including EMLA cream and vapocoolant spray (Spanos, et al. 2008).

# 2.0 Hypothesis and Specific Aims

Aim 1: Determine which pain management method, L.M.X.4 Cream vs. J-tip 1% Xylocaine MPF Injection, provides the greatest pain relief to infants with clubfoot undergoing an inoffice percutaneous TAL. Hypothesis: J-tip 1% Xylocaine MPF injection will provide equal or greater pain control when compared to L.M.X.4 cream in infants undergoing an in-office percutaneous TAL.

Aim 2: Determine if there is a difference in the rate of adverse events between the two pain management methods, L.M.X.4 Cream vs. J-tip 1% Xylocaine MPF Injection. Hypothesis: J-tip 1% Xylocaine MPF injection will not be associated with an increased rate of adverse events in comparison to L.M.X.4 cream in infants undergoing an in-office percutaneous TAL.

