#### Benefits

If it is determined that the utilization of the J-Tip system is equal to or more effective at reducing pain in infants undergoing a tenotomy than L.M.X.4 cream is, the potential benefits of this study may include better pain management in infants undergoing a tenotomy in the future. In addition, a reduction in the amount of time required to anesthetize the surgical area from 30 minutes with L.M.X.4 cream to 1-2 minutes with a J-Tip injection would decrease the overall length of the visit and cost of procedure, thus increasing quality, safety, and value.

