# 10.0 Statistical Considerations

# **Power Analysis**

A power analysis was conducted to determine the sample size needed to find a clinically meaningful difference of 2.5 point in the FLACC score (SD=3) between the two methods. With alpha=0.05, power=0.8, and and effect size d=.83, at least 24 patients per group are required (N=48). Assuming a 20% participant lost to follow-up rate, we will need to enroll 29 patients per group (N=58).

An interim power analysis was conducted to determine the sample size to find a clinically meaningful difference of 2.0 points in the FLACC score between the two methods. This was performed using the maximum SD of the FLACC score observations of the first 39 patients (SD=4.13). With alpha=0.05 and power=0.8, at least 47 patients per group are required (N=94).

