# Data Analysis

FLACC, heart rate, and oxygen saturation will be measured at 10 distinct time points (Table 1) during serial casting and following in-office TAL. Changes in FLACC score, heart rate, and oxygen saturation will be compared between treatment and control cohorts utilizing a two-way ANOVA with a Geisser-Greenhouse correction for matched time measures. A Sidak's multiple comparisons test will be utilized to assess differences between cohorts at each of the 10 time points assessed. To compare number of

complications between cohorts, data will be collected at 3-weeks post TAL and analyzed using a non-parametric Mann-Whitney test, given the ordinal nature of the data. Similar non-parametric analysis with correction for multiple comparisons between cohorts will be utilized to assess changes in responses to REDCap surveys. Statistical analysis will be conducted utilizing GraphPad Prism 8.3.0. Statistical significance will be p<0.05.

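### Both hypotheses claim the J-Tip is no worse, but the plan tests only for a difference and has no rule for reading a non-significant result

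*Combined protocol and SAP*

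**What the plan says.** Section 2.0 pairs each Aim with a hypothesis of a different kind. Aim 1 asks which method relieves pain most, while its hypothesis is that "J-tip 1% Xylocaine MPF injection will provide equal or greater pain control when compared to L.M.X.4 cream". Aim 2 is to "Determine if there is a difference in the rate of adverse events between the two pain management methods", while its hypothesis is that the J-Tip "will not be associated with an increased rate of adverse events in comparison to L.M.X.4 cream". Both hypotheses are statements that the J-Tip is no worse.

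Section 10.0, Power Analysis, gives two calculations, both for detecting a difference. The first uses 2.5 points and SD 3 and arrives at 24 per group. The second was run to "determine the sample size to find a clinically meaningful difference of 2.0 points in the FLACC score between the two methods", with SD 4.13 (the largest SD seen in the first 39 patients), and arrives at 47 per group, N=94.

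Section 10.0, Data Analysis, states: "Changes in FLACC score, heart rate, and oxygen saturation will be compared between treatment and control cohorts utilizing a two-way ANOVA". Sidak comparisons at 10 time points and a Mann-Whitney test on complications follow, all judged at p<0.05. No section gives a non-inferiority or equivalence margin, a confidence-interval rule, or a reading for a non-significant result.

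The Benefits text in Section 7.0 is also conditional on an equal-or-better finding: "If it is determined that the utilization of the J-Tip system is equal to or more effective at reducing pain".

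**The concern.** A significant result in favour of the J-Tip would support the *greater* half of the first hypothesis, and a significant result against it would refute that hypothesis. The gap is the outcome in between. Failing to reject no difference does not show equality, and the plan's only decision rule is a p-value threshold.

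That outcome is realistic. Of the trials summarised in Section 3.0, the one in infants (lumbar puncture) found no difference in pain score (p=0.58 and p=0.37). In the jet-injection versus ELA-Max trial, the blinded-observer comparison was also non-significant (p=0.23).

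If a null result were read as equal pain control, the trial could report equality when the J-Tip is worse by the 2.0 points that the plan itself calls clinically meaningful. The same holds for adverse events, for which the documents give no sample-size basis.

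**Working it through.** **Inputs.** Section 10.0, Power Analysis: differences of 2.5 and 2.0 points; SD 3 and 4.13; alpha 0.05; power 0.8; 24 and 47 per group. Section 10.0, Data Analysis: 10 time points, Sidak, p<0.05. Section 5.0: 94 patients at each site, with two clinics named. Section 12.0: 24 per group, N=48. Sidedness is not stated; two-sided is assumed.

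**1. The plan's own sample sizes.** n per group = 2(z₀.₉₇₅ + z₀.₈₀)² (SD/difference)², then adjusted to the t-test.
- First calculation: 2 × 7.849 × (3/2.5)² = 22.6; t-test 24. The stated 24 reproduces.
- Second calculation: 2 × 7.849 × (4.13/2.0)² = 66.9; t-test 68. The stated 47 does not reproduce. A one-sided 0.05 test would need 54, so sidedness does not explain it. At 47 per group, 80% power holds for 2.41 points at SD 4.13, or for SD 3.42 at 2.0 points.
- Power for 2.0 points at SD 4.13: 64% at 47 per group, 80% at 68, 91% at 94.

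**2. Chance of a non-significant result when the J-Tip is truly 2.0 points worse.** This is a proxy for the planned ANOVA: a two-sample t-test at one time point, using the noncentral t with noncentrality 2.0/SE and SE = SD√(2/n).

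| n per group | SD | Level | SE | Non-significant |
|---|---|---|---|---|
| 47 | 4.13 | 0.05 | 0.852 | 36% |
| 47 | 3 | 0.05 | 0.619 | 11% |
| 47 | 4.13 | Sidak, 0.0051 | 0.852 | 69% |
| 94 | 4.13 | 0.05 | 0.602 | 9% |

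The Sidak level is 1 − 0.95^(1/10) = 0.0051. Of the 36%, 20 points are what 80% power would allow; the other 16 come from the sizing shortfall in step 1. At Section 12.0's 24 per group the figure is 62% (SD 4.13, unadjusted).

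**3. What a CI adds.** At SD 4.13 and 47 per group, the 95% half-width is 1.986 × 0.852 = 1.69 points.
- An observed J-Tip disadvantage between 2.0 − 1.69 = 0.31 and 1.69 is non-significant, and its CI still includes 2.0.
- Below 0.31, a non-significant result excludes 2.0.
- At 94 per group the half-width is 1.19, and the corresponding range is 0.81 to 1.19.
- If the methods are truly equal, the upper limit falls below 2.0 with probability 0.642 at 47 per group and 0.910 at 94. Removing the 0.025 that are significant in favour of the J-Tip leaves 0.617 and 0.885. So about 62% and 89% of such trials would be non-significant and still exclude a 2.0-point disadvantage.

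**4. Two thresholds.** In the same proxy at 47 per group and SD 4.13, the Sidak test needs an observed difference of 2.868 × 0.852 = 2.44 points, while an unadjusted 95% CI excludes zero from 1.69. Between these values the two would disagree, so one must be named as governing.

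**5. Adverse events.** At an assumed 5% rate in both arms, the Wald half-width of the risk difference is 1.96√(2 × 0.05 × 0.95/47) = 8.8 percentage points, and 6.2 at 94 per group. With so few events Wald is unreliable: Newcombe with 2 of 47 in each arm gives about ±10.5.

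**The case against.** The strongest reply is that the tests match the Aims as written and that the hypotheses are loosely worded expectations. No section says that a null result will be reported as equal. That stands: the documents leave the reading open, and the harm is conditional on how the gap is filled.

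Several stronger readings are tempting and are not supported.
- A reader might infer that the sponsor plans to claim equality from p>0.05. The Benefits text speaks of an equal finding, but as a potential benefit and not as a decision rule.
- A reader might take 36% as the error rate of the planned analysis. It is a one-time-point proxy at the largest SD reported. SD 3 gives 11% and the Sidak level gives 69%.
- A reader might conclude that every non-significant result is inconclusive. Step 3 shows otherwise: many would exclude a 2.0-point disadvantage, which is why the remedy should rest on the CI.
- A reader might treat 2.0 points as a non-inferiority margin. The Power Analysis presents it only as a difference to detect.
- A reader might assume a particular change-score baseline. Data Analysis speaks of changes but defines no baseline. The Tenotomy section lists ten tenotomy-day measurements, which fits raw scores at each of 10 time points. This is not certain, because serial casting is also mentioned and Table 1 is not visible.

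It could also be said that the complication data, described as collected at 3 weeks, omit reactions on the day of tenotomy. The Tenotomy and adverse-event sections make a cumulative count the likelier reading, so this is a minor clarification. The sizing error is a separate defect, but it bears on this point because sample size determines what a null result can exclude.

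**Conclusion.** The concern holds in this form: both hypotheses say that the J-Tip is no worse, everything else in the plan addresses difference, and without a margin or CI rule a non-significant result cannot by itself support either hypothesis. This does not depend on the arithmetic; it would be true at full power.

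The size does depend on assumptions. For a true 2.0-point disadvantage at 47 per group, the proxy gives 11% to 69% non-significant results across the plan's two SDs and with or without the Sidak level (36% at SD 4.13, unadjusted). The 9% at 94 per group applies only if Section 5.0 means 94 at each of two sites. The SD of change scores is not given, so no figure is offered on that scale. The adverse-event figures rest on an assumed 5% rate.

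The stated 47 per group for 80% power is wrong on the plan's own inputs: it gives about 64%. The trial can run as designed, but these points should be settled before results by arm are seen.

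**What to change.** 1. Add to Data Analysis: *A p-value above 0.05 will not by itself be read as equal pain control or as no increase in adverse events. Non-significant results will be interpreted from the 95% CI; for pain, the report will state whether it excludes a J-Tip disadvantage of 2.0 FLACC points.* Then either reword the Section 2.0 hypotheses as difference hypotheses to match the Aims, or keep them and judge them by this CI. A formal non-inferiority margin is optional. If one is used, it must be justified and fixed without unblinded arm data.
2. For Aim 1, report the J-Tip minus L.M.X.4 difference in peak FLACC at incision with a two-sided 95% CI. Name it as the one estimate that governs the reading, with the Sidak comparisons at the 10 time points as supportive. If a change score is also shown, state that its baseline is the sponsor's choice.
3. For Aim 2, beside the planned Mann-Whitney test, add a risk difference for any local reaction or complication from cream application through day 21, with a 95% CI by a method suited to few events, such as Newcombe.
4. Reconcile Section 5.0 (94 at each site), Section 10.0 (N=94) and Section 12.0 (N=48). Restate the power of the chosen size for 2.0 points and SD 4.13: about 64% at 47 per group, 91% at 94. Settling all three on 47 per group would leave it at 64%.

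**Cost.** Items 1 to 3 need no new measurements and leave the planned tests in place. One time point must be named as governing, and a null result whose CI includes 2.0 can be reported only as inconclusive. Keeping 80% power takes 68 per group, or 136 in total before any loss to follow-up. That is 136 − 94 = 42 more than N=94, and none if Section 5.0 means 2 × 94 = 188 across both sites. Otherwise the plan need only state the lower power.

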# **Randomization**

The patients will be randomized in equal proportion (1:1) to either the *control* group (receive L.M.X.4 cream with J-Tip saline injection) or the *intervention* 

*group* (placebo cream with J-Tip with 0.25mL of 1% Xylocaine MPF). Randomization will take place on or after the final casting visit. A randomization allocation table created by statisticians will be uploaded into REDCap. The research coordinator will access the randomization module in REDCap and randomize the participant. Patients will not be randomized until they are definitively diagnosed with congenital idiopathic clubfoot that requires a tenotomy and consented for participation in the study.

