# Tenotomy

On the day of the subject's tenotomy they will receive pain control based on their group assignment- L.M.X.4 cream (with J-Tip Saline) or J-Tip with 0.25mL of 1% Xylocaine MPF (with placebo cream). The treating physician will provide a Dimeglio score. The following procedures will take place:

- Baseline: FLACC and pulse ox data will be recorded as baby is positioned on treatment table
- Application of randomized topical cream (either L.M.X.4 or placebo cream) for 30 minutes timed.
- Peak FLACC and pulse ox data will be recorded within 5 seconds of application of LMX 4 or Placebo Cream
- Consent for tenotomy procedure will be obtained (routine care).
- Baseline #2: FLACC and pulse ox data will be recorded 30 minutes after cream application
- Parents will leave room (routine care).
- Patient stays with healthcare staff (Physician, nurse, CCLS, cast tech, trained research assistant)
- Cream will be removed from the subject's foot (routine care). Peak FLACC and Pulse Ox will be recorded within 5 seconds after cream removal.
- Baseline #3: FLACC and pulse ox data will be recorded 30 seconds after cream removal
- J-Tip injection with 1% Xylocaine MPF or saline. Peak FLACC scale measurements and pulse ox measurements will be recorded within 5 seconds of injection (1st foot if bilateral)
- Following J-Tip injection there will be a 3-minute break, baby will be calmed during this time.
- Baseline #4: FLACC scale measurements and pulse ox measurements 3 minutes after J-Tip injection
- Tenotomy will be performed
  - FLACC Scale data and Pulse Ox data will be measured during the following events:
    - Percutaneous incision for TAL (1st foot if bilateral)- Peak FLACC scale and Pulse Ox data will be recorded within 5 seconds of poke of scalpel
    - Start of casting, after cast padding placed (1st cast if bilateral)

• End of casting (2nd cast if bilateral)

Adverse local effects of the cream and/or J-Tip injection will be noted (skin redness, swelling, rash, etc). Procedural complications will be recorded (excessive bleeding, concern for neurovascular injury, etc).

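### Both arms receive a jet injection, so Aim 2's between-arm comparison tests lidocaine product and route, not the J-Tip procedure against the cream procedure

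*Combined protocol and SAP*

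**What the plan says.** Section 2.0 sets Aim 2 as follows: "Determine if there is a difference in the rate of adverse events between the two pain management methods". Its hypothesis is that "J-tip 1% Xylocaine MPF injection will not be associated with an increased rate of adverse events in comparison to L.M.X.4 cream". The Benefits paragraph of section 7.0 shows the intended use. It anticipates "a reduction in the amount of time required to anesthetize the surgical area from 30 minutes with L.M.X.4 cream to 1-2 minutes with a J-Tip", which means a J-Tip in place of the cream.

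The arms are built differently. Under Randomization (section 5.0), controls "receive L.M.X.4 cream with J-Tip saline injection" and the intervention group has "placebo cream with J-Tip with 0.25mL of 1% Xylocaine MPF". The Tenotomy procedures in section 6.0 apply both components to everyone: "Application of randomized topical cream (either L.M.X.4 or placebo cream) for 30 minutes timed", then "J-Tip injection with 1% Xylocaine MPF or saline".

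On recording, the same list says: "Adverse local effects of the cream and/or J-Tip injection will be noted (skin redness, swelling, rash, etc". Section 10.0 (Data Analysis) compares the number of complications between cohorts with a Mann-Whitney test on data collected at three weeks, and compares the parent surveys between cohorts in a similar way. No summary of J-Tip-site events across all infants is planned.

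**The concern.** No infant has cream without a jet injection, and none has a jet injection without cream. Reactions to the jet as a procedure can occur in either arm, so a comparison of arms does not estimate how often the jet causes them. The same is true of wearing a cream for 30 minutes.

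Aim 2 is worded as a comparison of methods, and its hypothesis is a statement of no increase. A non-significant complication test would therefore invite the conclusion that replacing the cream with a J-Tip adds no adverse events. The randomised comparison does not address that question, and Aim 2 is one of only two stated aims.

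**Working it through.** **The plan's own figures.** The plan gives no event rate, margin or sample size for Aim 2, so there is nothing to reproduce for it. The 47 per group in the Power Analysis is set for FLACC and serves here only as a denominator. From its stated inputs, a two-sided calculation gives 2 × (1.96 + 0.84)² × (4.13/2.0)² ≈ 67 per group, not 47. That is a separate matter and does not affect what follows.

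**What is compared and what is envisaged.**

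| | Cream | Jet injection |
|---|---|---|
| Control arm | L.M.X.4 | saline |
| Intervention arm | placebo | lidocaine |
| Cream method as used | L.M.X.4 | none |
| J-Tip method as used | none | lidocaine |

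Neither trial arm matches either method as it would be used.

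**Model.** Assume independent causes. Let j be the risk from the jet itself, v the risk from wearing any cream, i the added risk from injected lidocaine, and c the added risk from L.M.X.4 over placebo cream.

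- Arm difference (intervention − control) = (1−j)(1−v)(i−c).
- Method difference (J-Tip alone − cream alone) = (1−v)(1−c) − (1−j)(1−i).

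If i = c, the arm difference is 0 and the method difference is (1−c)(j−v). Its sign depends on whether the jet or the cream-wearing causes more reactions.

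**Illustration.** All rates are assumed, since the documents give none: i = c = 5%, v = 0, 47 per arm. The last two columns are rejection probabilities of a two-sided Fisher test on any event, used as a stand-in for the planned test.

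| j | J-Tip alone v cream alone | Method difference | Arm difference | Rejects, this design | Rejects, if controls had no jet |
|---|---|---|---|---|---|
| 5% | 9.8% v 5% | 4.8 points | 0 | 1.6% | 5% |
| 10% | 14.5% v 5% | 9.5 points | 0 | 2.2% | 20% |
| 20% | 24.0% v 5% | 19.0 points | 0 | 2.8% | 67% |
| 30% | 33.5% v 5% | 28.5 points | 0 | 3.1% | 94% |

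**Unequal drug rates.** With j = 20%, i = 5%, c = 10% and v = 0, the arm difference is 0.80 × (0.05 − 0.10) = −4 points. The method difference is 0.90 − 0.80 × 0.95 = +14 points.

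**Cream-wearing effect.** With j = 5%, v = 10% and i = c = 5%, the arm difference is 0 and the method difference is 0.95 × (0.05 − 0.10) = −4.75 points. The two quantities can differ in either direction.

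**What the trial can say about the jet.** Every infant is injected, so J-Tip-site events can be described over all of them. With 0 events in n infants, the exact two-sided 95% upper limit is 1 − 0.025^(1/n):

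- n = 94: 3.8%
- n = 47 (one arm): 7.5%

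The denominator is not settled. Section 5.0 asks for 94 at each site and section 12.0 still says 48 in all. For n = 188 (two sites of 94) the limit is 1.9%, and for n = 48 it is 7.4%.

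**The case against.** The strongest reply is that Aim 2 names two drug products, and the arms do compare them. The test is informative about lidocaine-related events and about vehicle differences between the two creams and the two injectates. Section 2.0 does not force the reading that a method means the whole procedure. The Benefits paragraph supports that reading without compelling it. This stands, and it limits the point to the jet procedure.

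The plan also records more about the jet than its skin-effects line suggests. Peak FLACC and pulse oximetry are taken within 5 seconds of the injection in both arms, between Baseline #3 and Baseline #4. Section 8.0 requires reportable events to be listed individually with onset date, severity and relationship to study treatment. This stands too. It leaves a narrower gap: skin findings are not explicitly assigned to cream or jet, the relationship grade refers to study treatment as a whole, and no pooled device summary is planned. The case report forms are not in the documents, so they may record more.

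The double-dummy protects the blinding on which Aim 1 depends. Nothing here argues for removing it.

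**Conclusion.** The point holds as a mismatch between Aim 2's wording and what the randomised comparison estimates. A null complication result cannot support a claim of no increase for the J-Tip procedure as it would be used. The illustrated gap of 4.8 to 28.5 points rests on assumed rates and independent causes. The mismatch itself rests only on the arm definitions.

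A reader might infer three stronger things that the documents do not support:

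- *Aim 2 cannot be answered at all.* It can be, for lidocaine product and route.
- *The jet contributes exactly zero to the arm difference, whatever its rate.* That needs additive risks and the same jet effect with saline as with lidocaine. Under independent causes the jet rate already rescales the difference through (1−j), and an interaction between jet and lidocaine could show in the comparison.
- *The result is biased towards no difference, in favour of the device.* The −4 against +14 example reverses sign, and a cream-wearing effect can move the gap the other way. The accurate description is a different estimand.

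Should-fix: allocation, sample size and the between-arm test need not change.

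**What to change.** Keep the double-dummy and make three changes.

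1. Reword Aim 2 and its hypothesis so that the between-arm comparison concerns lidocaine product and route only: lidocaine by jet injection with placebo cream, against L.M.X.4 with a saline jet injection. State that it does not compare the J-Tip procedure with the cream procedure.
2. Add a descriptive table of J-Tip-site reactions in all injected infants. Count per infant (bilateral cases once), pooled and by saline or lidocaine jet, with exact 95% confidence intervals, and show cream-site reactions beside them. Reconcile the enrolment figures so that the denominator is clear.
3. To help attribution, record skin findings at Baseline #3 (30 seconds after cream removal, before the jet) and Baseline #4 (3 minutes after the jet, before the incision). State the limits: these checks catch only immediate reactions, a delayed cream reaction may first appear after the jet, and later reactions under the cast are missed. The zero-event limits would then apply to that short window.

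The cost is a narrower Aim 2 claim, two data fields and one table, with no added visits or patients.
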